5.1 Time and Events Table

	Baseline (T1)	Intervention	4 months post-baseline (T2)	Post-exit interview	
Screening	X	SCP vs ESCP			
Informed Consent	X				
Randomization	X				
Quality of Life	X			X	
Appraisal of prostate cancer symptoms	X			X	
Self-efficacy in symptom management	X			X	
Social support	X			X	
Health behaviors	X			X	
General symptoms	X			X	
Prostate cancer symptoms	X			X	
Comorbidities (Charlson index)	X			X	
Demographic characteristics	X				
Program satisfaction				X	
Perceived ease of use				X	
Participants' experiences of using the programs					X
Medical Records Abstraction	Continuously throughout study				

SUMMARY OF MEASURES AT BASELINE (T1) AND 4 MONTHS POST-BASELINE (T2)						
VARIABLES AND MEASUREMENT	DATA SOURCE A	GROUP	T1	T2	CRONBACH ALPHA	PERC PROGRAM ^C
Aim 1: Feasibility of ESCP						
Screening, Enrollment, and retention rates: research activity logs; field notes	AD	Both	X	X	na	na
Self-reported program use	PT, SP	Both		X	na	na
Web activity of using PERC: visit PERC or not, Number of logins, time spent on PERC, Use of modules and links	Tracking system	ESCP	X	X	na	
PERC session reviewed: # of reviewed sessions; % of reviewed sessions consistent with reported PCa symptoms	AD	ESCP		X	na	Built in tracking system in PERC
Program satisfaction and perceived ease of use: Usability Scale ^{82,83}	PT, SP	Both		X	na	na
Participants' experiences of using the programs: Exit Interview	PT, SP, AD	Both		X	na	na
Aim 2: Magnitude of benefits of ESCP for Survivor-Partner Couples (Compared with SCP only couples)						
MAIN OUTCOMES: Quality of Life (Overall, physical, emotional, and social well-being): Functional Assessment of Chronic Illness Therapy General Scale (27-item FACT-G) ^{82,101}	PT, SP	Both	X	X	0.90 ^{26,82}	All
Number of visits to post-treatment care services: Medical records	HER, PT	Both		X	na	All
Appraisal of PCa symptoms: 4-item Bother Questionnaire ^{25,26}	SP	Both	X	X	0.74-0.9 ^{25,26}	All
Self-efficacy in symptom management: 9-item Cancer Self-Efficacy Scale ¹⁰²	PT, SP	Both	X	X	0.91-0.96 ²⁵	All
Social Support: Adapted supportive interaction scale ¹⁰³	PT, SP	Both	X	X	0.74-0.86 ¹⁰³	PA; CR
Health behaviors: Physical Activity and Nutrition in Health Promoting Lifestyle Profile II. ^{104-107*}	PT, SP	Both	X	X	0.75-0.92 ^{106,107}	HB; CR
ANTECEDENTS (CONTROL VARIABLES): PARTICIPANT CHARACTERISTICS						
Demographic Characteristics: age, race/ethnicity, income, education, and etc.	PT, SP	Both	X		na	na
Type of PCa treatment: SCP record	PT	Both	X		na	na
Comorbidities: 13-item Charlson Comorbidity Index Brief ^{108,109}	PT, SP	Both	X	X	0.73-0.88 ¹⁰⁹	na
General symptoms: 21-item Risk of Distress General Symptom Scale ¹¹⁰	PT, SP	Both	X	X	0.76-0.84 ²²¹¹⁰	GS
PCa symptoms: Prostate cancer Index Composite (EPIC) ^{25,111}	PT	Both	X	X	0.74-0.90 ¹¹²	PCa
Note: a: PT=patient; SP=spouse/partner; AD=Administrative data and field notes; EHR=Electronic health record; b: both=participants in SCP only and ESCP groups; c: The content elements in PERC that will impact the outcomes. PCa=prostate cancer related symptoms; GS=general symptoms of pain, fatigue, sleep disturbance, emotional distress; HB=health behaviors (Mediterranean diet and walking); PA=post-session assignment; CR=online chat room; All=all elements in PERC (mentioned above).						

6.0 UNANTICIPATED PROBLEMS

6.1 Definition

As defined by UNC's IRB, unanticipated problems involving risks to study subjects or others (UPIRSO) refers to any incident, experience, or outcome that:

- Is unexpected (in terms of nature, severity, or frequency) given (a) the research procedures that are described in the protocol-related documents, such as the IRB-approved research protocol and informed consent document; and (b) the characteristics of the subject population being studied;
- Is related or possibly related to a subject's participation in the research; and
- Suggests that the research places subjects or others at a greater risk of harm (including physical, psychological, economic, or social harm) related to the research than was previously known or recognized.

We anticipate minimum risk of this study. The SCP and ESCP programs provide a series of resources that participants can use at their convenience. We will also refer them to their treating doctors and nurse practitioners should any serious event happen.

6.2 Reporting

Any unanticipated problem that occurs during the conduct of this study and that meets **at least** the first two criteria listed in 6.1 must be reported to the UNC IRB using the IRB's web-based reporting system.

7.0 STATISTICAL CONSIDERATIONS

7.1 Study Design

This is a two-group randomized controlled pretest-posttest design to test the feasibility of ESCP and estimate the magnitude of its benefits. Patients and their partners will be randomly assigned to the SCP (control) or ESCP (intervention) groups. Couples will complete baseline (T1, prior to randomization) and 4-month post-T1 follow-up measures (T2). Fifty men who recently complete initial treatment for localized prostate cancer and their partners will participate in this feasibility and proof-of-concept study.

behaviors from T1 to T2 among patients and partners, we use a two-sample t test with an effect size measured by Cohen's d .¹¹⁴ A sample size of 23 couples per group yields 80% power to detect a moderate/large effect size of 0.74 at the one-sided 0.05 significance level. Power calculations were performed using the **pwr** package in R (version 3.2.3).

We estimate power in testing our hypothesis that ESCP and SCP patients differ in the number of visits to post-treatment care services at T2 in the context of a Poisson regression model, using a right-tailed F test. Assuming that patients in the SCP only group average 6 post-treatment care visits at T2, a sample size of 23 patients per group yields 85% power to detect an increase or decrease of 33.3% in the average number of post-treatment care visits for patients in the ESCP group (i.e., 4 or 8 post-treatment care visits at T2) at the 0.05 significance level. Power calculations were performed using SAS Version 9.4.¹¹⁸

Due to the relative newness of SCPs and the complete novelty of ESCP for prostate cancer patients, we had no prior or historical information with regards to the difference between the SCP only and ESCP groups for these main outcomes. Therefore, we computed the effect sizes used for our power calculations based on the available sample size. We recognize that these effect sizes may not be reasonable guesses of the true effect sizes as a result, but due to budgetary concerns and time constraints, we thought it best to still proceed with our calculations.

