2.2 Secondary Objectives

To estimate the magnitude of benefit of ESCPs. Compared with SCP patients and partners, we hypothesize that ESCP patients and partners will report greater improvement, from T1 to T2, in QOL, self-efficacy in symptom management, social support, and health behaviors to manage symptoms. Compared with SCP partners, we hypothesize that ESCP partners will report greater improvement, from T1 to T2, in appraisals of prostate cancer symptoms. For conciseness, we list the measures for each of these five outcomes in the Summary of Measures table (Section 5.1). In addition, we hypothesize that ESCP and SCP patients will differ in the number of visits to post-treatment care services at T2.

The results obtained from our analysis of these outcomes will provide initial estimates of the magnitude and range of potential benefit of ESCP and will guide our planning for the size of a future, larger-scaled RCT that will definitively determine the benefit of ESCP for prostate cancer patients and their partners.

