We will fit a Poisson regression model, using a logarithm link function, to the number of patient visits to post-treatment care services at T2. In fitting this model, we will include group membership as a predictor, while controlling for the following effects: PCa treatment type (since this was our stratification variable when we randomly assigned patients to a specific group), age, income, and the Charlson Comorbidity Index, EPIC score, and the General Symptom Scale score at T2. Based on this model, we will estimate the ratio of the model-predicted number of visits to post-treatment care services at T2 for the ESCP group to that of the SCP only group to address the hypothesis that ESCP and SCP patients differ in the number of visits to post-treatment care services at T2.

To assess the effect of group on QOL, self-efficacy in symptom management, social support, and health behaviors while accounting for the fact that couples have correlated measurements, we will fit a series of linear mixed models across both patients and partners. Specifically, we will fit a linear mixed model to the change score for each measure of the outcomes of QOL, self-efficacy in symptom management, social support, and health behaviors. In doing so, we will include the following as fixed effects: group membership (ESCP vs. SCP), couple member (patient vs. partner), type of prostate cancer treatment (our stratification variable), the outcome's measure at T1, age, income, the Charlson Comorbidity Index score, and the differences in the Charlson Comorbidity Index, EPIC scores, and General Symptom Scale scores between T1 and T2. To account for the correlation among each patient and partner in a particular couple, we will also include couple membership as a random effect. Since appraisal of prostate cancer symptoms is only measured in partners and number of post-treatment care visits at T2 is only measured in patients, we cannot conduct these exploratory analyses for these two outcomes.

Since this is an exploratory proof-of-concept study, rather than a confirmatory study, we will not adjust for multiplicity when analyzing any of the previously mentioned outcomes. We expect the findings from

these analyses to be confirmed in future RCTs and that they may be used for generating hypotheses and designing new studies.

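### The 85% power stated for a 33.3% change in visits in either direction holds only for the decrease (6 to 4); for the increase (6 to 8) it is about 70–72%

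*Combined protocol and SAP*

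**What the plan says.** Section 2.2 sets a non-directional hypothesis for this outcome: "we hypothesize that ESCP and SCP patients will differ in the number of visits to post-treatment care services at T2". Section 7.2 repeats it and describes the power calculation as made "in the context of a Poisson regression model, using a right-tailed F test". The control assumption is "Assuming that patients in the SCP only group average 6 post-treatment care visits at T2", and the result is that "a sample size of 23 patients per group yields 85% power to detect an increase or decrease of 33.3% in the average number" of visits. The two alternatives are then written out: "i.e., 4 or 8 post-treatment care visits at T2) at the 0.05 significance level". The calculation is attributed to SAS 9.4.

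The analysis in section 7.3 matches that setting: "We will fit a Poisson regression model, using a logarithm link function", with group as the predictor and the effect expressed as a ratio of model-predicted visit numbers. Section 7.3 also states that visits are assumed to be Poisson when it describes how the future trial will be sized.

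**The concern.** Equal percentage changes up and down are not equal effects under a log link, and the Poisson variance changes with the mean as well. One power figure for both 6 to 4 and 6 to 8 is therefore suspect on its face.

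The hypothesis is that the groups differ, so the increase is part of what the plan claims to be able to detect. If its power is well below 85%, a non-significant result would be read as stronger evidence against increased care use than it is. Visits are listed among the main outcomes in the Summary of Measures (section 5.1), and section 7.3 intends to size the later trial for this outcome under the same Poisson assumption. The same symmetry assumption carried forward would leave that trial short of power for an increase.

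**Working it through.** **Inputs, all from the plan.** Control mean m0 = 6; ESCP mean m1 = 4 or 8; n = 23 per group; level 0.05 (section 7.2). Log link (section 7.3). Poisson counts with variance equal to the mean (section 7.3). The hypothesis is two-sided (sections 2.2 and 7.2). The right tail of an F test with 1 numerator df is two-sided on the log rate ratio, so the wording about a right-tailed test does not make it one-sided.

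**Formula.** Noncentrality = [ln(m1/m0)]² / [1/(n·m0) + 1/(n·m1)]. Power is then taken from the noncentral F with 1 and 2×23 − 2 = 44 df, or from its chi-square (normal) limit.

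**Decrease, 6 to 4 (the plan's figure).**
- ln(4/6) = −0.4055; squared, 0.1644.
- Variance = 1/138 + 1/92 = 0.01812.
- Noncentrality = 0.1644 / 0.01812 = 9.075.
- Power = 83.8% (F) or 85.4% (chi-square). The stated 85% is reproduced to within about a point.

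**Increase, 6 to 8.**
- ln(8/6) = 0.2877; squared, 0.08276.
- Variance = 1/138 + 1/184 = 0.01268.
- Noncentrality = 0.08276 / 0.01268 = 6.526.
- Power = 70.5% (F) or 72.4% (chi-square).

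The variance is smaller at 8 visits, but not by enough to offset the smaller log ratio.

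**Other ways of computing it, all with 23 per group.**

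| Calculation | 6 to 4 | 6 to 8 |
|---|---|---|
| F, 44 df, two-sided | 83.8% | 70.5% |
| F, 37 df (allowing seven further df for covariates), two-sided | 83.5% | 70.1% |
| Chi-square, two-sided | 85.4% | 72.4% |
| Likelihood-ratio noncentrality, F, two-sided | 84.5% | 70.9% |
| Difference scale, two-sided | 85.8% | 72.7% |
| Square-root scale, two-sided | 86.2% | 72.9% |
| Null variance at the control rate, two-sided | 89.6% | 67.7% |
| Exact conditional test, two-sided | 84.6% | 71.0% |
| Simulated Wald test, F critical value (1,000,000 runs) | 84.8% | 70.8% |
| F, 44 df, one-sided 0.05 | 90.7% | 80.8% |
| Chi-square, one-sided 0.05 | 91.4% | 81.9% |

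None gives 85% for the increase. The one-sided calculations miss 85% in both directions.

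**What would give 85% for an increase.** With 23 per group, a mean of 8.4 visits gives 84.0% (F) or 85.5% (chi-square), and 8.45 gives 85.3% (F). The detectable increase is therefore about +40% (8.4/6 = 1.40). To keep 6 to 8 and reach 85%, about 32 (chi-square, 85.4%) to 33 (F, 85.4%) analysable patients per group are needed.

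**The case against.** The arithmetic is hard to dispute, since sections 7.2 and 7.3 fix every input. The case on the other side is about weight.

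- *Little depends on the figure.* Visits are a secondary outcome in a feasibility pilot. The feasibility criterion in section 7.2 is 80% session consistency, section 7.3 calls the study exploratory, and the future trial is to be planned from the observed group means. This stands, and it limits the consequence.
- *The plan expects fewer visits.* Sections 2.0 and 4.3 aim at reduced use of care, and for that direction the stated power is about right. This also stands. The increase is nevertheless a case that section 7.2 chose to state, under a non-directional hypothesis.
- *The plan already warns the reader.* Section 7.2 says that the effect sizes were derived from the available sample and may not be realistic. That caveat is about whether the effects are plausible. It does not cover a wrong power for the effects as given.
- *The 23 per group looks out of date.* It fits 50 couples (25 × 0.92 = 23), while section 7.2 gives a total of 70. With 35 × 0.92 ≈ 32 completers per group, the increase would have 84.3% (F) or 85.4% (chi-square). So correcting the sample size would largely remove the shortfall. As printed, however, the sentence ties 85% to 23 per group, and with 32 the decrease would be about 94%, so a single figure would still not serve both directions.
- *How the 85% arose is not documented.* The pattern is what one would see if the figure for the decrease had been used for both, but that is an inference and the conclusion does not need it.

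**Conclusion.** The concern holds. With 23 patients per group, the stated 85% is right to within about a point for a fall from 6 to 4 visits (83.8% by F, 85.4% by chi-square) and overstated by about 13 to 15 points for a rise from 6 to 8 (70.5% and 72.4%). The chance of missing a true rise to 8 is about 28–30%, against the 15% that the text implies.

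This rests on the plan's own assumptions: exactly Poisson counts, a control mean of 6, a two-sided 0.05 test and no covariate effect on precision. Overdispersion or covariate adjustment could change both powers, but the stated calculation includes neither, so they cannot explain the figure. The error affects the reported power of one exploratory secondary outcome. It alters no analysis and no decision rule.

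**What to change.** Replace the single figure in section 7.2 with one for each direction, and name the method. For the F test that the plan specifies (44 df, 23 per group, 0.05): about 84% power for a decrease from 6 to 4 and about 70% for an increase from 6 to 8. The chi-square limit gives 85% and 72%. Alternatively, keep 85% and give the detectable increase as about 8.4 to 8.45 visits (roughly +40%).

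If the number of completers is revised to 32 per group to agree with the total of 70 couples, restate the powers as about 94% for the decrease and 84–85% for the increase. When the later trial is sized, compute each direction separately.

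The cost is one sentence, with no change to the design or analysis. The stated power for an increase becomes less favourable if 23 per group is kept.

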7.3 Data Analysis Plans

Primary Objective: Qualitative data will be analyzed to help explain quantitative findings.¹¹⁵ First we will use a quantitative and qualitative mixed method to analyze the data.¹¹⁵ We will examine research activity logs and field notes to compute enrollment, recruitment, and retention rates that will be reported by group and by time point, along with 95% confidence intervals (CI). These results will provide useful information in planning scenarios for subsequent studies. Descriptive statistics (including percentages, means, standard deviations) and their corresponding 95% CIs will also be computed for feasibility measures relating to web activity, percentage of PERC sessions reviewed that are consistent with the symptoms patients reported, as well as for self-reported use of programs and the usability scale for couples in both groups. Due to the fact that this is an exploratory proof-of-concept study, rather than a confirmatory study, we will not adjust for multiplicity when computing the CIs for these feasibility measures.

Interview data will be coded in Atlas.ti by the PI and the project coordinator using thematic analysis^{116,117} based on a priori codes from our interview guide—a method we have used in a past study.¹⁴ Members of the research team will have discussions to reconcile coding discrepancies. The responses will be analyzed based on features of PERC that are intended to make it feasible as well as participants' experiences using SCP/ESCP, to help identify the barriers and facilitators that are unique to the ESCP users. These findings will help improve PERC as well as the use of SCPs and ESCPs.

Secondary Objectives: For patients and partners in the SCP only and ESCP groups, descriptive statistics will be calculated at T1 for the measures of the following outcomes: QOL, appraisal of prostate cancer symptoms, self-efficacy in symptom management, social support, and health behaviors; at T1, descriptive statistics will be calculated for the measure of appraisal of prostate cancer symptoms for partners in both groups (see Summary of Measures table for description of the measures used for these outcomes). They will also be computed for all participant characteristics (see Summary of Measures table). At T2, descriptive statistics will also be calculated in both groups for these outcomes, the number of patient visits to post-treatment care services, and the scores for the Charlson Comorbidity Index, EPIC and the Risk of Distress General Symptom Scale. These statistics will include the mean, standard deviation, minimum, median, and maximum for each continuous variable, and frequencies and percentages for each categorical variable.

All analyses will be conducted using an intention-to-treat approach, in which all randomized participants will be analyzed according to their assigned group, regardless of the extent of intervention actually received.

For patients and partners separately, we will first use the Shapiro Wilk test to determine whether the distribution of the change score (i.e., change from T1 to T2) for the measures of each of the following main outcomes significantly differs from that a normal distribution: QOL, self-efficacy in symptom management, social support, and health behaviors. If so, we will apply a power transformation to that change score to help satisfy the assumption of normal error terms that is integral to linear models. We will then fit an analysis of covariance (ANCOVA) model to the change score for each outcome, including an indicator variable for group membership (ESCP vs. SCP only) as a predictor and the outcome's baseline (T1) measure as a covariate. In this model, we will also control for the effect of PCa treatment type (surgery, radiation, and radiation + hormonal therapy) because we stratified on PCa treatment type when we randomly assigned each couple to either the ESCP or the SCP only groups. We will also include the following participant characteristics as covariates: age, income, and the differences in the Charlson Comorbidity Index, EPIC scores, and General Symptom Scale scores between T1 and T2. We thought it appropriate to include these characteristics as covariates because they have been shown to be related to QOL and the other main outcomes. For each of these change scores, we will estimate the contrast between its model-predicted value for the ESCP group versus the SCP only group to address the hypothesis of greater improvement in QOL, self-efficacy in symptom management, social support, and health behaviors for the ESCP group.

Since the main outcome of appraisal of PCa symptoms was only measured in partners, we can only analyze it among partners. Otherwise, we will use the same approach to analyze it as we did for QOL, self-efficacy in symptom management, social support, and health behaviors.

We will fit a Poisson regression model, using a logarithm link function, to the number of patient visits to post-treatment care services at T2. In fitting this model, we will include group membership as a predictor, while controlling for the following effects: PCa treatment type (since this was our stratification variable when we randomly assigned patients to a specific group), age, income, and the Charlson Comorbidity Index, EPIC score, and the General Symptom Scale score at T2. Based on this model, we will estimate the ratio of the model-predicted number of visits to post-treatment care services at T2 for the ESCP group to that of the SCP only group to address the hypothesis that ESCP and SCP patients differ in the number of visits to post-treatment care services at T2.

To assess the effect of group on QOL, self-efficacy in symptom management, social support, and health behaviors while accounting for the fact that couples have correlated measurements, we will fit a series of linear mixed models across both patients and partners. Specifically, we will fit a linear mixed model to the change score for each measure of the outcomes of QOL, self-efficacy in symptom management, social support, and health behaviors. In doing so, we will include the following as fixed effects: group membership (ESCP vs. SCP), couple member (patient vs. partner), type of prostate cancer treatment (our stratification variable), the outcome's measure at T1, age, income, the Charlson Comorbidity Index score, and the differences in the Charlson Comorbidity Index, EPIC scores, and General Symptom Scale scores between T1 and T2. To account for the correlation among each patient and partner in a particular couple, we will also include couple membership as a random effect. Since appraisal of prostate cancer symptoms is only measured in partners and number of post-treatment care visits at T2 is only measured in patients, we cannot conduct these exploratory analyses for these two outcomes.

Since this is an exploratory proof-of-concept study, rather than a confirmatory study, we will not adjust for multiplicity when analyzing any of the previously mentioned outcomes. We expect the findings from

these analyses to be confirmed in future RCTs and that they may be used for generating hypotheses and designing new studies.

To aid in planning the sample size of a future, larger-scaled RCT, standardized effect sizes for the change scores (from T1 to T2) in the measures of QOL, self-efficacy in symptom management, social support, and health behaviors will be calculated, for patients and partners separately, as the ratio of the mean difference in each change score between the ESCP and SCP groups to its standard deviation. For partners only, we will compute this standardized effect size for the change score in appraisal of prostate cancer symptoms. For patients only, we will compute the mean number of patient visits to post-treatment care services for each group. Based on our assumption that the number of patient visits follows a Poisson distribution, this information will allow us to determine the sample size that will provide sufficient power to test the hypothesis that ESCP and SCP patients differ in the number of visits to post-treatment care services at T2.

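### A normality test on raw change scores, not model residuals, triggers an unspecified power transformation that takes the adjusted ESCP-SCP contrast off the original score scale

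*Combined protocol and SAP*

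**What the plan says.** Section 7.3 (Secondary Objectives) sets out a two-stage rule, applied to patients and partners separately. The first stage reads "we will first use the Shapiro Wilk test to determine whether the distribution of the change score (i.e., change from T1 to T2", and covers QOL, self-efficacy, social support and health behaviors. The second stage follows a significant result: "If so, we will apply a power transformation to that change score to help satisfy the assumption of normal error terms". ANCOVA is then fitted to the change score with group, baseline value, treatment type, age, income and several T1-to-T2 differences as predictors, and "we will estimate the contrast between its model-predicted value for the ESCP group versus the SCP only group". Partner appraisal of symptoms is handled in the same way.

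The section gives no significance level for the normality test, no power family or exponent, no shift for zero or negative values, and no back-transformation.

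Three other places bear on the scale of the result:
- Section 2.2 says the results "will provide initial estimates of the magnitude and range of potential benefit of ESCP".
- For the couple-level analysis, Section 7.3 says "we will fit a linear mixed model to the change score for each measure of the outcomes" and mentions no transformation.
- For planning the next trial, Section 7.3 defines "standardized effect sizes for the change scores (from T1 to T2) in the measures of QOL" and the other outcomes as "the ratio of the mean difference in each change score between the ESCP and SCP groups to its standard deviation", again with no transformation.

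**The concern.** There are two faults.

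**The rule tests the wrong quantity.** The stated reason is normality of the error terms. The distribution of raw change also carries the treatment effect, the baseline value and every other covariate. It can look non-normal when the errors are normal, and it can hide errors that are not. Because the two arms are pooled, whether the outcome is transformed depends partly on the effect being estimated.

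**A triggered transformation changes what is estimated.** A contrast of powered change scores is not in score points. Each outcome is tested separately in patients and in partners, so the same instrument could be reported in points for one role and in transformed units for the other. Neither would necessarily line up with the mixed model. That model pools both roles and cannot sensibly take a response transformed in one role only.

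At stake is whether the adjusted contrasts can be read as magnitudes of benefit, which is what Section 2.2 wants from them.

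**Working it through.** **Inputs from the plan.** 23 couples per group analysed, d = 0.74, one-sided alpha 0.05, power 80% (Section 7.2). The documents give no SD and no change-score distribution, so every distribution below is an assumption, as is alpha 0.05 for Shapiro-Wilk.

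**1. The plan's own figure.** Noncentrality = 0.74 × √(23/2) = 0.74 × 3.391 = 2.51 on 44 df. One-sided power of the t test is 0.796, which reproduces the stated 80% (two-sided: 0.689). It is computed on the untransformed scale.

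**2. How many changes are zero or negative.** For a normal change score, P(change ≤ 0) = Φ(-mean/SD).

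| mean/SD | share ≤ 0 |
|---|---|
| 0 | 50% |
| 0.25 | 40% |
| 0.5 | 31% |
| 0.74 | 23% |
| 1.0 | 16% |

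Even at mean/SD = 1.0, the chance that all 46 are positive is about 0.0004. The simulated ANCOVA scenarios in step 4 give roughly 25-45% at or below zero.

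**3. What common powers do to such values.** Take changes of -8, -3, 0, 2, 5.
- Exponents 0.5 and 1/3 are undefined for the two negatives.
- Exponent -1 is infinite at 0.
- Squaring gives 64, 9, 0, 4, 25, so a worsening of 8 ranks above a gain of 5.
- Unshifted Box-Cox stops because the data must be positive.
- Yeo-Johnson runs and preserves order.

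**4. Raw change against residuals.** Model: change = 0.2 + slope × standardised baseline + 0.74 × group + error, with 23 per arm and within-arm SD 1. At slope -0.5 the residual SD is √(1 - 0.25) = 0.866; at slope -0.8 it is √(1 - 0.64) = 0.6. Skewed baselines are exponential or lognormal (sigma 1); skewed errors are gamma with shape 2.

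| Scenario | Rejects on raw change | Rejects on residuals |
|---|---|---|
| Skewed baseline, normal errors, slope -0.5 | about 9-17% | about 5% |
| Skewed baseline, normal errors, slope -0.8 | up to about 50% | about 5% |
| Skewed errors, slope -0.5 | about 37% | about 86% |

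**5. Dependence on the treatment effect.** With gamma (shape 4) errors and no baseline term, the raw-change test fires in 67%, 44% and 20% of data sets for group differences of 0, 0.74 and 1.5 SD. On group-centred residuals it fires in about 62% throughout. With 35 per group (70 couples, 1:1), the raw figures are 86%, 63% and 32%, against 82-83% on residuals.

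**6. Mixed scales.** The named outcomes give 4 × 2 roles + partner appraisal = 9 tests. If all nine change scores were normal and independent, the chance of at least one trigger would be 1 - 0.95^9 = 37%. The outcomes are correlated, so this is only a guide.

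**7. What happens to the contrast.** Assume gamma (shape 4) data, SD 10 points, true difference 7.4 points, 23 per group, triggered data sets only, simple group difference. The mean raw contrast is 7.5 points. After shifting the minimum to 1, 5 or 20 and raising to the fitted power, it is 0.91, 0.32 or 0.04 in transformed units. At the shift to 20 the mean fitted power is negative (-0.30), which reverses order, and the mean standardised contrast goes from +0.73 to -0.66. That sign change would not arise with the Box-Cox scaling, which divides by the exponent; the loss of units would remain.

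**8. Error rate and power.** In the skewed-error scenarios, untransformed ANCOVA holds type I error at 4.6% and two-sided power at about 80%. (Baseline adjustment raises the effective difference to 0.74/0.866 = 0.85 residual SDs, hence 80% two-sided here.) The gate followed by Yeo-Johnson keeps type I error near 5% and power at 80-84%.

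**The case against.** The best defence is that the plan prescribes no bad transformation. It says only that a power transformation will be used to help normality, and a competent analyst would choose Yeo-Johnson or a shifted Box-Cox. Step 8 shows that such a choice is valid and can gain a little power. The original scale also survives elsewhere: Section 7.3 reports descriptive statistics by group at T1 and T2, and its planning effect sizes mention no transformation. The analyses are exploratory, and naming a family with back-transformation would also meet the interpretability problem.

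Much of this stands, and it rules out three stronger readings.
- A reader might infer that the rule is undefined or non-monotone as such, or that it would drop participants. That holds only for ordinary unshifted powers. The plan does not call for them, and dropping people would conflict with its intention-to-treat statement.
- A reader might infer a collapse in power, because squaring every change score takes power from 80% to about 32% with normal errors. The plan transforms only after a significant test. Squaring only then gives 77% against 80%, and squaring is an unlikely way to seek normality.
- A reader might infer that planning of the next trial is compromised. The planning effect sizes appear to stay on the change-score scale, so it is not necessarily affected.

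The defence does not answer the other two points. The test is still run on the wrong quantity, and any non-linear family, however well chosen, still moves the adjusted contrast off the score scale for whichever outcomes and roles happen to trigger.

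**Conclusion.** The point holds as a fault of specification and interpretability. The gate checks raw change when its own rationale concerns model errors, and under assumed distributions it errs in both directions: about 9-17%, and up to about 50% in a steeper scenario, where 5% is expected; and about 37% where the residual test gives 86%. The transformation it triggers is unspecified and leaves the adjusted contrast in units that may differ between outcomes and roles, and from the mixed models and effect sizes in the same section.

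The consequence is moderate. It falls on the adjusted ANCOVA contrasts of a secondary, exploratory analysis. With a monotone family neither type I error nor power is harmed. The trigger rates depend on the assumed baseline shape, slope and residual SD, none of which the documents supply. The loss of scale does not depend on them.

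**What to change.** In Section 7.3, delete the Shapiro-Wilk step and the conditional power transformation. State instead that the baseline-adjusted ANCOVA is fitted to the untransformed change score for every outcome, in patients and in partners, and that the ESCP-SCP contrast is reported in score points with a 95% CI. Check normality on the model residuals, graphically. If they are clearly non-normal, add one pre-specified sensitivity analysis: bootstrap or heteroscedasticity-robust intervals, a rank-based ANCOVA, or a transformed analysis with its family, shift and back-transformation fixed in advance. State that the mixed models and planning effect sizes use the same untransformed scores.

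This changes wording only, with no effect on sample size or data collection, and the power calculation in Section 7.2 is already on the untransformed scale. The downside is a possible small loss of power against a well-chosen transformation when errors are skewed (about 80% against 84%).
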